3.4.4. Subgroups analysis

In addition, descriptive statistics at each concerned visit of the reference ulcer area, linear advance of the wound margin towards the wound centre and reference ulcer volume will be performed.

Except for the linear advance of the wound margin towards the wound centre, the relative change from baseline (change for volume) will also be described.

These description will be performed in the FAS in the following subgroups:

- Combined prognosis criteria on size and age of the ulcer ($\leq 10 \text{ cm}^2$ and ≤ 6 months / $> 10 \text{ cm}^2$ or > 6 months) at baseline.
- Size of the ulcer at baseline ($\leq 20 \text{ cm}^2$ / $> 20 \text{ cm}^2$).
- Size of the ulcer at baseline ($\leq 50 \text{ cm}^2$ / $> 50 \text{ cm}^2$).
- Diabetes status (yes/no).

If a subgroup contains less than 20 patients, only listings will be provided for this subgroup.

3.5. Exploratory analysis

Not applicable.

3.6. Safety analysis

All safety analyses will be performed in the SS on the taken IMP treatment, by treatment group over the W000-W006 period.

Only for adverse events, in addition, an analysis will be performed on post treatment intake (i.e after last treatment intake date + 15 days (excluded)).

General definitions are provided in Section 3.1.2. Specific definitions are provided in Appendix 5.2. and provided in the Specifications document.

3.6.1. Adverse events

Definition:

- Treatment Emergent Adverse Events (TEAE) are defined as all adverse events:
 - which occur between the first IMP intake date (included) and the last IMP intake date + 15 days (included)or
 - which occur before the first IMP intake date and which worsen (in terms of intensity) or become serious according to the investigator's opinion between the first IMP intake date (included) and the last IMP intake date + 15 days (included).

Note: + 15 days is calculated according to the half-life of the S42909.

Of note, in case of multiple information of the same event before the first IMP intake date, the information nearest to the first IMP intake date is taken into account.

The seriousness of the adverse event and the relationship with the IMP are based on the investigator's opinion but often also include the sponsor's decision to upgrade the seriousness and/or relation to the IMP (see TLG for details).

Analyses:

The number of events, the number and percentage of patients reporting at least one event, presented by primary system organ class (SOC) and/or preferred term (PT) (depending of the analysis) will be provided for :

- Serious AE over the study period according to the investigator's or sponsor's opinion.
- Treatment emergent AE (TEAE), TEAE leading to IMP withdrawal, TEAE requiring new treatment or increase of ongoing treatment, TEAE requiring surgical or medical procedure, TEAE related to IMP, serious TEAE, severe TEAE, non serious TEAE over the treatment period (EUDRACT), After treatment AE.

TEAE will be described according to the seriousness, the intensity, the relationship with the IMP, the action taken regarding the IMP, the requirement of added therapy and the outcome.

The medical concept of diarrhea, *i.e.* TEAE related to diarrhea, will be analysed through a listing. The MedDRA code list to use is the list n°3741 Diarrhoea medical concept M22.0.

A listing of deaths and ERIN will be provided.

A Listing of AE occurring after the treatment period will also provided.

The following information will be taken into account:

- For the analyses where the intensity of the adverse event is considered, the worst intensity from the day of emergence to the end of the studied period will be taken into account.
- For the analyses where the action taken regarding the IMP is considered, all the actions taken recorded from the day of emergence to the end of the studied period will be taken into account.
- For the analysis of recovered emergent adverse events during the treatment period, an EAE is considered as recovered "during treatment period" if the associated outcome is "recovered" or "recovered with sequelae" and occurs between the first IMP intake date and the last IMP intake date + 15 days (included).

3.6.2. Clinical laboratory evaluation

For all parameters, the **dosing of samples come from local laboratories**. So no quantitative analysis will be performed. In the qualitative analysis, data will be compared to reference ranges provided by these local laboratories.

Definition:

- A laboratory value is considered as analysable if non-missing and not flagged in the ClinTrial database as "not analysable".

Analyses:

For each biochemical and haematological parameter, the following analyses will be performed:

- Number and percentage of patients with at least one high/low emergent abnormal value under treatment, according to the laboratory reference ranges and to the cut-offs for PCSA values.

- Laboratory parameters classified (number and percentage of patients in each class) according to these reference ranges and cut-offs, and using shift tables from baseline to the worst (high and/or low) values under treatment.

Moreover, listings of patients with out-of-range or PCSA analysable values emergent under treatment and of non-analysable values excluded from analyses will be provided.

Urinary parameters will be described in classes (absent, trace, +, ++, +++, +++) at baseline and at each post-baseline visit under treatment.

3.6.3. Vital signs, clinical examination and other observations related to safety

3.6.3.1. Vital signs and clinical examination

Definition:

The following vital signs and clinical examination will be analysed during the study:

- Weight (kg).
- BMI (kg/m²).
- Sitting Systolic Blood Pressure (SBP) (mmHg).
- Sitting Diastolic Blood Pressure (DBP) (mmHg).
- Sitting heart rate (bpm).

Analysis:

They will be described, in terms of value at baseline, value at each post-baseline visit under treatment as well as in terms of change from baseline to last post-baseline visit under treatment.

3.6.3.2. Electrocardiogram

Definition:

- All non-missing values are considered as analysable.

The following ECG parameters will be analysed:

- Presence of clinically significant ECG abnormalities (yes/no).
- PR interval (msec).
- QT interval (msec).
- RR interval (msec).
- Duration of QRS (msec).
- QTcF - Fridericia's Correction Formula (msec).
- Sinus Rhythm (yes/no).

Emergence of clinically significant ECG during the treatment period:

- When no ECG is judged as clinically significant at baseline and the clinical significance appears between the first IMP intake date (included) and the last IMP intake date + 15 days (included)

Analyses:

ECG parameters will be described, in terms of values at baseline, values at each post-baseline visit under treatment and last post-baseline values under treatment; as well as, for quantitative criteria, in terms of change from baseline to each post-baseline visit under treatment and to last post-baseline visit under treatment and in term of emergence of clinically significant ECG.

Moreover, values at each visit and changes from baseline of QTcF interval will be described in classes, considering thresholds defined in ICH E14 (*i.e.*, ≤ 450 , $]450; 480]$, $]480; 500]$ and > 500 msec for values at each visit and ≤ 30 , $]30; 60]$ and > 60 msec for changes from baseline to each visit).

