5.6. Participant withdrawal

5.6.1. Withdrawal criteria

Information to be collected during the last visit of these participants is given in [section 5.6.2](#). These follow-up modalities are used to ensure the efficacy and safety evaluation of all participants who received the IMP.

The reasons for premature discontinuation of IMP are:

- Adverse events or any condition that would jeopardise participants' safety and is incompatible with continuation of the IMP according to the judgement of the investigator. These include:
 - **ALT or AST increase > 3 times the ULN value**, after 2 consecutive tests performed 7 days apart.
 - **Total bilirubin increase > 2 times the ULN value**, after 2 consecutive tests performed 7 days apart.
 - **CPK increase > 5 times the ULN value**, after 2 consecutive tests performed 7 days apart.

- **Clinically significant anaemia** defined by an haemoglobin level < 10g/dL and a decrease ≥ 1.5 g/dL in men and ≥ 1 g/dL in women compared to previous value.
- **QTcF > 500 ms, or QTcF > 480 ms with increase in QTcF > 60 ms as compared with QTcF at selection period**, confirmed by a repeated ECG, with measurements validated by a cardiologist.
- Clinically significant adverse event related to the cardiovascular system for which, in the judgement of the investigator, continuation of the IMP could constitute a risk for the safety of the participant.
- **Severe uncontrolled diarrhoea with risk of dehydration.**
- **Major deviation to the protocol or any medical condition incompatible with continuation of the IMP treatment** (including pregnancy) **or preventing the analysis of the primary endpoint** (e.g. non-compliance with standardized compression regimen or with protocol requirements or study-related procedures).
- Any medical event requiring administration of an unauthorised concomitant treatment (see [section 6.3](#)).
- **Non-medical reason** (e.g. withdrawal of participant's consent), which should be carefully documented.
- **Lost to follow-up** (see [section 5.6.3](#)).

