ECG parameters and ECG abnormalities will be described at each visit.

Biomarkers

The association between healing and plasma biomarkers could be investigated with prognostic approaches e.g. regression models, Receiver Operating Characteristic (ROC) curve.

In order to study the association between genomic criteria and efficacy or safety of S42909, exploratory analyses using single-marker and multi-marker approaches could be used.

[figure not shown]

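### The SAP states QTcF threshold classes only visit by visit; it plans no per-patient maximum QTcF, maximum increase or count of patients meeting the protocol's QTcF limit

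*SAP*

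**What the plan says.** SAP 3.6.3.2 fixes the time basis of the QTcF classes: "Moreover, values at each visit and changes from baseline of QTcF interval will be described in classes, considering thresholds defined in ICH E14". Values are split at 450, 480 and 500 ms. Changes are split at 30 and 60 ms, the top class being "and > 60 msec for changes from baseline to each visit". The remaining ECG summaries cover baseline, "values at each post-baseline visit under treatment and last post-baseline values under treatment", and the matching changes. One further item counts patients whose ECG becomes clinically significant on treatment when it was not so at baseline.

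Protocol 10.1.4 is also by visit: "ECG parameters and ECG abnormalities will be described at each visit".

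Two other places use a per-patient basis:

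- Protocol 5.6.1 lists among its reasons for stopping IMP "QTcF > 500 ms, or QTcF > 480 ms with increase in QTcF > 60 ms", relative to the selection period, confirmed on a repeat ECG and validated by a cardiologist.
- SAP 3.6.2, for biochemistry and haematology, plans "Number and percentage of patients with at least one high/low emergent abnormal value under treatment" and classifies patients "using shift tables from baseline to the worst (high and/or low) values under treatment".

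**The concern.** The safety profile of each dose, ECG included, is a stated secondary objective (protocol 3.2, SAP 1.1). For QTcF the natural per-dose question is how many patients ever crossed a threshold. The planned class tables answer a different one: how many were above it at a given visit. The same patient may appear in several rows, or each row may hold a different patient, and the table looks the same either way. A dose-related excess spread over visits would then read as isolated values. A last-value summary does not help, because it misses a prolongation that has resolved.

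Value classes and change classes are also separate tables. The second limb of the 5.6.1 limit, which needs both conditions in the same patient, cannot in general be read from them.

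The SAP already counts each patient at the worst value for laboratory data. Those data come from local laboratories, and the SAP's table of versions says that ECGs are not centralised either, so local reading does not by itself explain the different treatment.

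**Working it through.** The documents state no expected QTcF exceedance rate, so there is no planned figure to reproduce. The check is what the by-visit tables can and cannot determine.

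**Inputs**

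- Patients: 121 included (SAP 1.3) in six arms. Equal split assumed: 121/6 = 20.2, about 20 per arm.
- Post-baseline ECGs: W001, W002, W003, W004, W006 and W008, so six (protocol Table (4.2.2) 1 and section 8.2).
- Window: a value is under treatment up to last intake + 15 days (SAP 3.1.2). W008 is 14 ± 4 days after W006 (protocol 6.1), that is 10 to 18 days. A W008 visit on days 16 to 18 falls outside for a completer, so five or six ECGs count.
- Per-visit risk of crossing a threshold: not in the documents. 3% is assumed, with 1% to 5% as the range.

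**Step 1: from rows to patients.** Suppose each of k visit rows shows one patient with an increase above 60 ms. The number of distinct patients is anywhere from 1 to k.

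- Same patient throughout: 1/20 = 5%.
- Different patients, k = 5: 5/20 = 25%.
- Different patients, k = 6: 6/20 = 30%.

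**Step 2: the same in rates.** With per-visit risk p, the per-patient risk is p if the same patients recur and 1 − (1 − p)^6 if six visits are independent.

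| Assumed p | Full recurrence | Independence, six visits |
|---|---|---|
| 1% | 1% | 5.9% |
| 2% | 2% | 11.4% |
| 3% | 3% | 1 − 0.97^6 = 16.7% |
| 5% | 5% | 26.5% |

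With five visits and p = 3%, independence gives 1 − 0.97^5 = 14.1%. Repeat ECGs in one person are correlated, so the truth lies between the two columns. Every row of the by-visit table would show about p in either case.

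**Step 3: the combined limb of 5.6.1.** At one visit with n patients, let a be above 480 ms and b have an increase above 60 ms. The number with both lies between max(0, a + b − n) and min(a, b). With a = b = 2 and n = 20 that is 0 to 2. It is fixed only when a or b is zero, or when one class holds the whole arm. The entry limit does not close the gap: a confirmed QTcF above 450 ms excludes (protocol 5.4), and 480 − 450 = 30, so crossing 480 ms from an eligible baseline guarantees only an increase above 30 ms.

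**The case against.** A reader might infer that the study report will be unable to say how many patients had a QTcF prolongation, or that such patients will go unseen. The documents do not support that.

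- The table templates and the Specifications are separate documents (SAP 1 and 3.6) and were not available. They may contain a maximum-value table. What can be said is that the SAP and protocol text plan none.
- Some cases are captured per patient and by arm. A clinically significant ECG abnormality must be recorded as an adverse event (protocol 8.2). The SAP tabulates patients with treatment-emergent events and with events leading to IMP withdrawal (3.6.1), withdrawal reasons by arm (3.2.1) and new clinically significant ECGs (3.6.3.2). This stands, but these routes depend on judgement or reporting, and none is tabulated by QTcF threshold.
- The 1-to-6 range is weakest for the stopping limit itself. A patient with a confirmed exceedance should stop IMP, and so should not recur over six rows. The range in Step 1 concerns the 60 ms increase alone, which is not a stopping limit. This stands.
- It is also tempting to say that repeat ECGs have no place in the tables. The SAP does not say so. It treats all non-missing values as analysable and is silent on how repeats are assigned to visits.
- The 17% figure is the independence extreme of an assumed 3%; the other end is 3%.
- The laboratory comparison is not exact. Laboratory data get no quantitative analysis, whereas ECG data get values and changes at every visit. Vital signs and urinalysis also have no worst-value summary. The SAP already goes beyond the protocol by adding QTcF classes.
- ECGs are read locally and may be 6- or 12-lead. A maximum over several readings will push more patients over a threshold in every arm, placebo included.

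No QT signal is alleged. Protocol section 2 reports no clinically relevant ECG findings in earlier studies.

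**Conclusion.** The point holds as a gap in the stated analysis. No maximum QTcF, maximum increase or count of patients meeting the 5.6.1 limit is planned in the SAP or protocol text, and the by-visit classes cannot supply these counts. In an arm of about 20, identical by-visit tables are compatible with 5% or with 25% to 30% of patients ever exceeding a 60 ms increase. At an assumed 3% per-visit risk, the per-patient figure runs from 3% to about 17% over six visits. These sizes rest on an equal split of 121 patients, on five or six ECGs counting as under treatment, and on assumed rates; they illustrate the ambiguity and do not predict a result.

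The consequence is limited to the descriptive per-dose ECG safety summary. The primary analysis, type I error, power and data collection are unaffected.

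**What to change.** Add to SAP 3.6.3.2, by dose group in the Safety Set:

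- the number and percentage of patients by maximum QTcF class and by maximum increase class, using the existing cut-offs, over all ECGs under treatment, scheduled and repeat;
- the number and percentage of patients meeting the existing QTcF criterion of protocol 5.6.1, stating whether the count uses confirmed readings, since that criterion requires a repeat ECG.

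Keep the by-visit tables. If the templates already contain such a table, one sentence in the SAP settles the matter.

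The cost is SAP wording and one extra table from data already collected. The drawback is the upward pull of a maximum over several locally read ECGs, so each dose should be read against placebo and not against zero.

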3.7. Biomarkers analysis

Not applicable.

4. INTERIM ANALYSIS

Not applicable.

5. APPENDICES

5.1. General analytic definitions

Definitions below correspond to calculation rules for first and last IMP intake dates and other general definitions.

5.1.1. First and last IMP intake dates

For patients having taken at least one dose of IMP over the period between W000 and W006, the dates of first and last IMP intake on the analysis period will be defined as follows:

- The date of the first IMP intake at the first visit performed within the analysis period.
- The date of the last IMP intake at the last visit performed within the analysis period.

Note: Visits with both missing first and last IMP intake dates and with number of returned tablets equal to number of tablets delivered at the previous visit (or with estimated number of tablets taken equal to 0) will not be taken into account.

After selection of the dates of first and last IMP intake as defined above, if these dates are missing or incomplete, substitution rules will be applied to identify baseline value, values under treatment and emergent adverse events.

5.2. Specific analytic definitions and data handling conventions

5.2.1. Disposition and baseline characteristics

Disease duration and reference ulcer duration

The disease duration according to the first leg ulcer (days) is defined as:

Date of selection visit (ASSE) – Date of diagnosis of the first leg ulcer

The reference ulcer duration according to the patient (days):

Date of selection visit (ASSE) – Date of occurrence or recurrence of the reference ulcer according to patient

The reference ulcer duration according to the physician (days):

Date of selection visit (ASSE) – Date of diagnosis or recurrence of the reference ulcer by the physician

Reference ulcer duration according to the physician will also be described in classes defined as:

If $(\text{disease duration (days)}/30.44) \leq 6$ then disease duration in class = ‘ ≤ 6 months’.

If $(\text{disease duration (days)}/30.44) > 6$ then disease duration in class = ‘ > 6 months’.

The reference ulcer duration according to the physician in classes is used for the **subgroup**.

CEAP classification (Clinical-Etiology-Anatomy-Pathophysiology)

Presence of an obstruction or a reflux in each type of veins (superficial veins and deep veins) will be derived with:

- **Superficial veins** will be defined as:

Telangiectasies or reticular veins; Great saphenous vein above knee; Great saphenous vein below knee; Small saphenous vein and Nonsaphenous veins.

- **Deep veins** will be defined as :
Inferior vena cava; Common iliac vein; Internal iliac vein; External iliac vein; Pelvic: gonadal, broad ligament veins, other; Common femoral vein; Deep femoral vein; Femoral vein; Popliteal vein Crural: anterior tibial, posterior tibial, peroneal veins (all paired) and Muscular: gastrocnemial, soleal veins, other.
- **Presence of an obstruction** is defined if the classification in (« Obstruction » or « Reflux and obstruction ») is completed.
- **Presence of a reflux** is defined if the classification in (« Reflux» or « Reflux and obstruction ») is completed.

Medical history other than studied disease and surgical or medical procedures history

The existence of a history (Yes/No) is defined from the presence, or not, of a Primary system organ class (SOC) and/or Preferred term (PT).

No specific medical and surgical histories or medical procedures are defined.

Previous treatments

The previous treatments are the treatments for venous leg ulcers taken within 6 months before selection, or any previous treatments which could interfere with the IMP or the study assessments in the last 6 weeks before the selection with associated stop date strictly inferior to the first IMP intake date (W000).

Note: In case of patient included and/or randomised but not treated (*i.e.* patients with treatment duration equal to 0), the previous treatment is defined as any treatment with an associated stop date strictly inferior to the date of the inclusion visit.

Only treatment with an Anatomical Therapeutic Chemical (ATC) classification and/or a Preferred name is considered.

No specific previous treatments are defined.

The compliance of compression stocking

The compliance of compression stocking (%) for each period (W000-W004 and W000-W006 periods) is defined as:

(Sum of number of days of stockings wearing / Sum of number of days when stockings had to be worn) x 100 (for the considered period)

with:

- Number of days of stockings wearing = Number of days of stockings wearing.
- Number of days when stockings had to be worn = Last visit date - First visit date, in days (for the considered period)

Note: Compliance is not calculated in case of missing information.

5.2.2. Treatments of patients

Global duration

Global duration (days) is defined as:

Date of the last visit – Date of selection visit + 1

Extent of exposure and treatment compliance

The treatment duration (days) for each period (W000-W004 and W000-W006 periods) is defined as:

Date of the last IMP intake (for the considered period) – Date of the first IMP intake (for the considered period) + 1

Notes:

- For patients with no dose of IMP (for the considered period), the duration is null.
- For patients with missing or incomplete date of first or/and last IMP intake (for the considered period) before substitution, the duration is not calculated.

The treatment exposure (days) for each period (W000-W004 and W000-W006 periods) is defined as:

Treatment duration – Overall duration of interruption

with the overall duration of interruption defined as: Sum of (Date of IMP restarted – Date of last IMP intake before interruption – 1 (*)).

(*) or the number of days of interruption in case of missing or incomplete date of IMP restarted or date of last IMP intake before interruption.

The treatment compliance (%) for each period (W000-W004 and W000-W006 periods) is defined as:

(Sum of number of tablets taken / Sum of number of tablets to be taken) x 100 (for the considered period)

with:

- Number of tablets taken = Estimated number of tablets taken, or if not completed, Number of tablets dispensed - Number of tablets returned (for the considered period).
- Number of tablets to be taken = The formula is different depending on the concerned period because of the following points:

The last tablets to be taken during the W000-W004 period are the 6 tablets (3 in the morning and 3 in the evening) the day before the visit W004, whereas the last tablets to be taken during the W000-W006 period are the 3 tablets in the morning of the visit W006 after the PK predose sampling at the site.

Of note that the visit W003 is the only visit to which patients have to take the 3 tablets in the morning before the visit W003. For the other visits, the patient have to take the 3 tablets in the morning after the PK predosesampling at the site.

- For the W000-W004 period, number of tablets to be taken:

For withdrawn patients at W003:

Number of tablets prescribed per day x [Last visit date - First visit date, in days] + Number of tablets prescribed for the morning of the visit W003

For other patients:

Number of tablets prescribed per day x [Last visit date - First visit date, in days]

- For the W000-W006 period, number of tablets to be taken :

For completers or withdrawn patients at W003:

Number of tablets prescribed per day x [(Last visit date - First visit date), in days] + Number of tablets prescribed the last morning (i.e., 3 tablets)

For withdrawn patients at other visits than W003:

Number of tablets prescribed per day x [(Last visit date - First visit date), in days]

Note: Compliance is not calculated in case of missing information.

Concomitant treatments

The **existence of a concomitant treatment** (Yes/No) is defined from the presence, or not, of an Anatomical Therapeutic Chemical (ATC) classification and/or Preferred name.

The **periods** considered **for the analysis** are:

- **At inclusion** for which treatments with start date \leq inclusion date and stop date \geq inclusion date or missing are taken into account.
- **During the treatment period** for each considered period (W000-W004 and W000-W006) for which treatments:
 - with start date \geq first IMP intake date and $<$ last IMP intake date (for the considered period), or
 - with start date \leq first IMP intake date and stop date \geq first IMP intake date or missing are taken into account.
- **After the last IMP intake** for which treatments:
 - with start date \geq last IMP intake, or
 - with start date \leq last IMP intake date and stop date $>$ last IMP intake date or missing are taken into account.

Concomitant treatments could be considered in one or several of the possible analysis periods.

